2.6.4 Supportive analyses

In order to mitigate the impact of missing data of UPDD (HSS, ISS), model based approach will be applied if applicable. A linear mixed model with repeated measures (MMRM) will be used to estimate treatment differences for change from baseline in UAS7 score up to the end of study, based on the SAF. The MMRM model will include [REDACTED], visit week, baseline UAS7 score and interaction of baseline UAS7 score by visit week as fixed effects. Repeated measures within subject are modeled using an unstructured covariance of the error terms. If the model does not converge, the compound symmetry covariance structure will be used. For details, please see the Appendix.

For HSS7 and ISS7, same analyses will be performed.

[REDACTED]
The SAS program code and is described in section 5.5.2.

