1.2 Study objectives and endpoints

Objective(s)	Endpoint(s)
Primary objective(s)	Endpoint(s) for primary objective(s)

The primary objective of this study is to investigate the safety and tolerability of ligelizumab 120 mg q4w for 12 months	
Overall safety data, assessed as treatment emergent adverse events during the study
Secondary objective(s)	Endpoint(s) for secondary objective(s)

To evaluate the efficacy of ligelizumab 120 mg q4w by evaluation of:
UAS7, HSS7 and ISS7 change from baseline over timeAchievement of the complete UAS7 = 0, HSS7 = 0 and ISS7 = 0 response over timeProfile of change from baseline in the Dermatology Life Quality Index (DLQI)Achievement of DLQI = 0/1 by visit up to end of study	
Absolute change from baseline of UAS7, HSS7 and ISS7 by visit up to end of studyProportion of subjects with UAS7 = 0, HSS7 = 0, and ISS7 = 0 response by visit up to the end of studyAbsolute change from baseline of DLQI by visit up to end of studyProportion of subjects with DLQI = 0/1 by visit up to end of study

2 Statistical methods

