2.1.1 General definitions

Study day and Study week based on eDiary

Study day is defined as the number of days since the date of first dose of study medication. The date of first dose of study medication is defined as Day 1 and the day before the first dose of study medication is defined as Day -1.

Therefore, for a particular date, study day will be calculated as follows:

- for dates on or after the first date of study medication,
Study day = Assessment date – Date of first dose of study medication + 1;
- for dates prior to the first date of study medication,
Study day = Assessment date – Date of first dose of study medication.

For event dates on or after Day 1, study day for a particular event date will be calculated as [Date of event] - [Date of first dose] + 1. For the dates before Day 1, study day for an event date will be calculated as [Date of event] - [Date of first dose].

Duration of an event will be calculated as (Event end date - Event start date + 1).

The study weeks are defined based on the study days starting with Day 1 (see [Table 2-1](#)), which is the day the patient receives the first study treatment.

The study week defined in this section will be used for the efficacy analyses based on the eDiary.

Table 2-1 Study Week definition based on Study Day of eDiary

Study Week	Study Days
Baseline	(-7)-(-1)
1	1-7
2	8-14
x	$7 \times (x-1) + 1 - 7 \times x$
64	442 – 448

For the by visit summary tables, they will include all the information collected at the scheduled visit. The unscheduled visit information will not be included in the by visit summary table. No remapping visit will be provided.

Study Week based on RaveX collected visit information

For the by visit summary tables (lab results, ECGs, vital signs, PROs, [REDACTED] etc..) , all the information collected at the scheduled visit will be included for the analyses. Unscheduled visit information will not be included in the by visit summary descriptive statistics. The unscheduled visit information will be only included in the maximum or minimum post treatment assessment summaries.

Baseline

In general, baseline is defined as the last measurement (including unscheduled visits) prior to or on the first dose of study drug at Day 1. Refer to the baseline definitions for each analysis described in the later sections.

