2.6.3 Handling of missing values/censoring/discontinuations

The UAS7 score is derived from the sum of the HSS7 score and the ISS7 score, as noted above. If ISS7 or HSS7 is missing, UAS7 will also be missing. The HSS7 and ISS7 score will be derived by adding up the daily HSS and ISS scores of the 7 days preceding the visit, respectively. The daily score (HSS and ISS) will be calculated by averaging the morning and evening HSS

and ISS score, respectively. If one of the morning or evening scores is missing, the non-missing score for that day (morning or evening) will then be used as the daily score.

For each weekly score from the UPDD (i.e. HSS7, ISS7), if one or more of the daily scores are missing, the following principles will be applied to handle the missing data:

- If a patient has at least 4 non-missing daily (morning or evening) scores within the 7 days prior to the study visit, the weekly score will be calculated as the sum of the available eDiary scores of that week, divided by the number of non-missing days, multiplied by 7.
- If there are less than 4 non-missing daily scores within the prior 7 days, then the weekly score will be considered as missing for that week.

Duplicate data handling of questionnaires

For HSS7, ISS7, the daily score is derived from the average of morning and evening scores (e.g. in case HSS is entered twice in the morning at different times).

All other questionnaires (i.e. other than HSS and ISS) are completed either daily or at visits. If any of those questionnaires are completed more than once per day or visit (depending on the questionnaire schedule), then the worst outcome (i.e. the highest score) of the duplicate observations will be used in the analysis.

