5.5.2 Key Secondary analysis

Mixed model with repeated measures (MMRM):

The supportive analyses for UAS7, HSS7 and ISS7 will be performed.

The SAS procedure proc mixed will be used for this analysis with the following code:

```
proc mixed data=..... order=internal covtest;  
class subject week cuind;  
model change = baseline week cuind baseline*week / s ddfm=kr;  
repeated week / type=un subject=subject;  
lsmeans week / cl e OM;  
ods output LSmeans=mean ConvergenceStatus=convtest;  
run;
```

where change = change from baseline UAS7 score

baseline = baseline UAS7 score

week = study week

[REDACTED] [REDACTED]

subject = subject

If the computation of the MMRM model takes extreme amount of time, the ddfm=bw option could be considered. If the model with an unstructured covariance matrix does not converge, SAS will give a warning as “Unable to make hessian positive definite” or “Unable to Converge” or “stopped because of infinite likelihood”. Meanwhile, the Status variable in the convtest dataset created will take on the value 0 or 1. In this case, the compound-symmetry structure should be used, by replacing type=un in the above codes with type=cs.

If after this step the model still does not converge, remove the covariates in the following order until it converges: baseline*week, [REDACTED]

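### The MMRM text says visit week but its code says study week (1–64); as coded, the unstructured covariance cannot be estimated with about 65 subjects, leaving only compound symmetry

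*SAP*

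**What the plan says.** SAP 2.6.4 plans a mixed model for repeated measures on UAS7, repeated for HSS7 and ISS7, to reduce the effect of missing diary data up to the end of study. The visible fixed effects are "visit week, baseline UAS7 score and interaction of baseline UAS7 score by visit week as fixed effects", and "Repeated measures within subject are modeled using an unstructured covariance of the error terms". Two other sections also point to visits. SAP 2.6.3 derives the weekly scores by "adding up the daily HSS and ISS scores of the 7 days preceding the visit", and SAP 1.2 lists "Absolute change from baseline of UAS7, HSS7 and ISS7 by visit up to end of" study.

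The program in SAP 5.5.2 has a repeated statement over week with type=un and defines "week = study week". Study week is a defined term. Table 2-1 in SAP 2.1.1 numbers seven-day blocks from Week 1 to Week 64, and "The study week defined in this section will be used for the efficacy analyses based on the eDiary". UAS7, HSS7 and ISS7 are eDiary scores.

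If the unstructured fit fails, "the compound-symmetry structure should be used, by replacing type=un in the above codes with type=cs". The only later step visible is removal of covariates. On degrees of freedom, the one relaxation is: "If the computation of the MMRM model takes extreme amount of time, the ddfm=bw option could be considered".

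SAP 2.6.4 also describes the estimand as differences between treatments. The trial has one arm, and the code requests only least-squares means by week.

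**The concern.** A programmer who follows the text fits 16 time levels; one who follows the code and Table 2-1 fits 64. SAP 2.6.2 does not settle it, because it allows tables by visit or by week. The choice decides whether the specified covariance can be fitted at all. With 64 levels and about 65 subjects there are too few subjects to estimate an unstructured matrix, and the plan then moves directly to compound symmetry. That structure assumes one variance and one correlation across early, on-treatment and off-treatment weeks.

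At stake is the only visible model-based method for missing weekly scores; the rule in SAP 2.6.3 covers only missing entries within a week. As written, a reader cannot tell which model will be reported. If the variance changes over time, compound symmetry can misstate the weekly confidence intervals.

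**Working it through.** **Inputs.** About 65 subjects in one arm (SAP 1.1). 58 with post-baseline UAS7 and SD 13 (SAP 3.2). 64 study weeks (SAP Table 2-1). 16 scheduled post-baseline visits, Weeks 4, 8, ..., 64: 13 up to Week 52 and 3 in follow-up (Protocol Table 8-1). Mean model: intercept and baseline slope for each week, plus cuind (SAP 5.5.2).

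**The plan's own figure.** 1.96 × 13/√58 = 3.35, given as 3.3, so −22.0 ± 3.3 = (−25.3, −18.7). This reproduces; with the t quantile the half-width is 3.42. The SAP gives no figure for the size or estimability of the MMRM covariance.

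**Size and rank.** An unstructured matrix on T levels has T(T+1)/2 parameters. With an intercept and a baseline slope fitted at each week, the residual cross-product has rank at most N − 2. If N − 2 < T the matrix is singular and the likelihood has no maximum at a positive-definite covariance. The ranks below were confirmed numerically on complete simulated data.

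| Time factor | Parameters | Rank, N = 65 | Rank, N = 58 |
|---|---|---|---|
| 64 study weeks | 64 × 65/2 = 2,080 | 63 of 64 | 56 of 64 |
| 16 visit weeks | 16 × 17/2 = 136 | 16 of 16 | 16 of 16 |

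**Subjects needed.** Under monotone dropout, level k is regressed on k − 1 earlier levels, an intercept and baseline. That is k + 1 coefficients, so at least k + 2 subjects must be observed at level k: 18 for k = 16 and 66 for k = 64, one more than the 65 planned. Counting cuind as a further subject-level covariate raises 66 to 67. Allowing 10% dropout, 66/0.9 = 73.3, so about 74 would have to be enrolled.

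**Effect of compound symmetry (illustration).** The documents give one SD (13) and no weekly profile. Suppose the SD rises linearly from 8 at Week 1 to 13 at Week 12 and then stays flat. The variances for Weeks 1–12 sum to 1,352.5 and those for Weeks 13–64 to 52 × 169 = 8,788. The pooled SD is √(10,140.5/64) = 12.59. Pooled SD divided by weekly SD is:

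- Week 1: 12.59/8 = 1.57
- Week 4: 12.59/9.36 = 1.34
- Week 8: 12.59/11.18 = 1.13
- Weeks 12–64: 12.59/13 = 0.97

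If baseline explains 0% or 30% of the variance, differing between early and late weeks, the Week 1 ratio ranges from 1.33 to 1.87.

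**Simulation.** Assumptions: 65 subjects; correlation 0.4 + 0.6 × 0.9^lag; dropout depending on the last weekly score, about 9% by Week 52; 2,000 runs for compound symmetry (Monte Carlo SE about 0.5 points) and 1,500 for unstructured.

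| Model | SD | Model SE / true SE | 95% CI coverage |
|---|---|---|---|
| Compound symmetry, 64 weeks | 13 throughout | 0.95–0.99 | 94.0–95.0% |
| Compound symmetry, 64 weeks | 8 to 13 | 1.56 (Wk 1), 1.32 (Wk 4), 0.96–0.97 (Wks 12, 52, 64) | 99.8%, 99.1%, 94.3–95.3% |
| Unstructured, 16 weeks | 8 to 13 | 0.97–0.99 (Wks 4, 12, 52, 64) | 94.1–95.3% |

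The 16-week unstructured model converged in all 1,500 runs. With 3% intermittent missing added it converged in 200 of 200, with as few as 51 subjects observed at Week 52.

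**The case against.** The strongest reply is that the failure depends on one reading. Table 2-1 maps diary days to week numbers and does not say that all 64 weeks enter the model. The label in SAP 5.5.2 may be loose wording, the input dataset is left blank, and the prose points to visits. On that reading the model is estimable. This is fair as far as it goes: the singularity is conditional on 64 levels. But study week is a defined term assigned to eDiary efficacy analyses, so taking the code literally is legitimate, and the SAP must say which reading it means.

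Second, non-convergence is already handled by a written rule that lists an infinite likelihood among its triggers. True, so an analysis would be produced. It would be compound symmetry, though, reached by a step that at the planned size is close to certain.

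Third, the documents show no material harm. With SD 13 at every week compound symmetry performs well. The larger errors come from an assumed SD path and fall in early weeks, where intervals are too wide. This stands. The scenario also keeps the SD flat after Week 12, so a change in variance off treatment was not tested.

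Fourth, redaction limits what can be said. Parts of SAP 2.6.4 and 5.5.2 are blacked out, so claims that something is the only method hold for the visible text. Leaving cuind out of the rank check does not help the plan, since a further covariate only raises the number of subjects needed. Enrolment is approximate, and 66 or 67 fully complete subjects would just reach full rank with a nearly singular matrix, but the plan itself assumes 10% missing.

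**Conclusion.** The point holds. Text and code name different repeated factors, and the coded one cannot support the unstructured covariance at the plan's own numbers: rank 63 of 64 with 65 complete subjects, 56 of 64 with 58. The text version, with 136 parameters on 16 weeks, is estimable at both sizes. The rank result depends only on the number of levels, the number of subjects and the mean model.

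The numerical consequence is less certain. It ranges from negligible (constant SD) to a Week 1 standard error 33–87% too large (assumed SD path from 8 to 13, with the stated range for baseline). The stated estimand, a difference between treatments, cannot exist in a single-arm trial.

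This should be corrected, but it does not threaten the trial's conclusions. The analysis is supportive and applied only if applicable, nothing is formally tested, the primary endpoint is adverse events, and the one-sample t intervals in SAP 2.6.2 do not use this covariance.

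**What to change.** 1. In both SAP 2.6.4 and 5.5.2, define the repeated factor as the 16 scheduled post-baseline weeks (4, 8, ..., 64). For visits on their nominal days this agrees with Table 2-1: study Week 4 is Days 22–28, the seven days before the Day 29 visit.
2. If the unstructured fit does not converge, try heterogeneous Toeplitz, then heterogeneous AR(1). Keep compound symmetry as the last step, with empirical (sandwich) standard errors and compatible degrees of freedom such as ddfm=bw. Widen the permission for ddfm=bw, which now covers only extreme run time.
3. Describe the target as mean change from baseline at each week.

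The cost is some SAP wording and a few lines of code. Scores from weeks between visits, including Weeks 1–3, leave the model and stay in the descriptive weekly tables. With known covariance, 7 of 65 subjects dropping out and four correlation settings, the Week 52 standard error is 0.3–0.4% larger than with all 64 weeks. Sandwich errors in the last fallback would not remove bias in the means if compound symmetry is wrong. If the sponsor does want all 64 weeks, the unstructured start must be replaced by a structure that 58 to 65 subjects can support.

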2.7 Safety analyses

For all safety analyses, the SAF will be used.

2.7.1 Adverse events (AEs)

Refer to the AEs analyses described in [Section 2.5](#) in this document.

2.7.1.1 Crude and Exposure-Adjusted Incidence Rate

The crude incidence rate is defined as the percentage of subjects with a specific adverse event divided by the total number of subjects.

Due to expected differences in exposure and follow-up due to varied duration of study participation between participants, adverse event incidence rates will be provided as “exposure adjusted AE incidence rates (EAIRs)” in addition to the crude incidence.

The EAIR is defined as the number of subjects with a specific event divided by the total exposure-time among the subjects in the study group. That is, the EAIR is calculated as:

$EAIR = n / \sum t_i$, where n is the number of subjects having the i^{th} type event, and t_i is a subject's exposure time and defined as the shortest of the following:

- 1) time to the first episode of the i^{th} type event (if the event occurs),
- 2) duration of study treatment plus the 16-week washout period (approximately corresponding to five half-lives) after last treatment dose, or
- 3) end of the analysis period (week 64 for all safety follow-up).

The total exposure time of all subjects in a treatment group is $\sum t_i$. The EAIR is interpreted as the number of events occurring in a population per unit time. The exact Poisson 95% confidence interval for the EAIR will be provided as well, where an exact $100*(1-\alpha)\%$ confidence interval will be derived as follows (Garwood 1936, Sahai and Khurshid 1993):

- Lower confidence limit $L = \frac{0.5C_{\alpha/2,2n}}{\sum t_i}$ for $n>0$, 0 otherwise,
- Upper confidence limit $U = \frac{0.5C_{1-\alpha/2,2n+2}}{\sum t_i}$,

where $C_{\alpha,k}$ is the α th quantile of the Chi-square distribution with k degrees of freedom.

Whenever applicable, exposure adjusted incidence rates will be provided for the type as below:

1. TEAE and TESAE: Primary SOC level, PT level
2. TEAE of special interest

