1.1 Study design

This is a Phase III multi-center, open-label, single arm study. The study consists of 3 distinct periods:

- Screening period (Day -28 to Day -14): Duration of up to 4 weeks in which subjects who have given informed consent are assessed for eligibility.
- Treatment period (52 weeks): The subjects will be seen in the clinic every 4 weeks.
- Post-treatment follow-up period (12 weeks): This period consists of a subject visit in the clinic every 4 weeks with the final visit (Visit 1999) occurring 16 weeks after the last treatment dose.

Figure 1-1 Study design

This study is designed to obtain safety data of QGE031 in 65 Japanese CSU patients. Details of sample size are described in [Section 3](#) in this document.

The study population will consist of approximately 65 male and female subjects aged ≥ 18 years who have been diagnosed with CSU and who remain symptomatic despite the use of H1-AH.

It is anticipated that approximately 81 subjects will need to be screened (an estimated screening failure rate of 20%) in order to enroll approximately 65 subjects into the 52 week treatment period (see [Figure 1-1](#)).

No randomization is planned in this study.

The primary objective of this study is to investigate the safety and tolerability of ligelizumab 120 mg q4w for 12 months.

The primary variable is the number and percentage of patients who reported treatment emergent adverse events during the 64 week (treatment period+ follow-up period) study period.

No interim analysis is planned in this study.

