2.3.1 Patient disposition

For each study epoch (i.e., screening period, treatment period, follow-up period), the overall number of patients who entered, completed, and discontinued that phase will be summarized including the reasons for discontinuation.

The number of patients included in each analysis set will be tabulated, as well as the reasons for exclusions from SAF. Patient exclusion from analysis sets will be listed for all patients with reasons for exclusion.

The number of patients with protocol deviations will be tabulated by category (e.g., selection criteria not met, prohibited concomitant medication, key procedures not performed as per protocol) and deviation for the SAF. Protocol deviations will be listed, deviation and analysis populations from which patients are excluded.

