2.5.1 Primary endpoint

The primary variable is the number and percentage of patients who reported treatment emergent adverse events during the 64 week study period.

All adverse events which start after the first dose of study medication and within 16 weeks of the last dose will be considered as a treatment emergent adverse event.

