2.5.3 Handling of missing values/censoring/discontinuations

For the subject who discontinued treatment or study, no imputation or adjustment will be considered for counting the number of subjects who have a treatment emergent AE/SAE. All subjects will be treated equally when the data is summarized, regardless of the treatment duration and/or study duration of each subject.

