5.2.2 AE date imputation

Rules for imputing the AE end date:

- If the AE end date month is missing, then the imputed end date should be set to the earliest of the study end date, 31DECYYYY or date of death.
- If the AE end date day is missing, then the imputed end date should be set to the earliest of the study end date, last day of the month or date of death.
- If AE year is missing or AE is ongoing, then the end date will not be imputed.

Rules for imputing the AE start date:

- If imputing end dates, then this should be done prior to calculating imputed start dates.

The following table explains the notation used in the logic matrix. Please note that **missing start dates** will not be imputed.

	Day	Month	Year
Partial Adverse Event Start Date	Not used	MON	YYYY
Treatment Start Date	Not used	TRTM	TRTY

The following matrix explains the logic behind the imputation.

	MON MISSING	MON < TRTM	MON = TRTM	MON > TRTM
YYYY MISSING	(1) No convention			
YYYY < TRTY	(a) Before Treatment Start	(b) Before Treatment Start	(b) Before Treatment Start	(b) Before Treatment Start
YYYY = TRTY	(a) Uncertain	(b) Before Treatment Start	(c) Uncertain	(c) After Treatment Start
YYYY > TRTY	(a) After Treatment Start	(b) After Treatment Start	(b) After Treatment Start	(b) After Treatment Start

Before imputing AE start date, find the AE start reference date.

1. If the (imputed) AE end date is complete and the (imputed) AE end date < treatment start date, then AE start reference date = min(informed consent date, earliest visit date).
2. Otherwise, AE start reference date = treatment start date.

Impute AE start date:

1. If the AE start date year value is missing, then the date uncertainty is too high to impute a rational date. Therefore, if the AE year value is missing, then the imputed AE start date is set to NULL.
2. If the AE start date year value is less than the treatment start date year value, then the AE started before treatment. Therefore:
 - a. If AE month is missing, then the imputed AE start date is set to the mid-year point (01JulYYYY).
 - b. Otherwise, if AE month is not missing, then the imputed AE start date is set to the mid-month point (15MONYYYY).
3. If the AE start date year value is greater than the treatment start date year value, then the AE started after treatment. Therefore:
 - a. If the AE month is missing, then the imputed AE start date is set to the year start point (01JanYYYY).

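### Exposure-adjusted AE rates: person-time has no stop at study exit or death, so event-free early leavers add unobserved time

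*SAP*

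**What the plan says.** SAP 2.7.1.1 gives this reason for adding the EAIR to the crude incidence: "Due to expected differences in exposure and follow-up due to varied duration of study participation between participants". The rate is n divided by the sum of t_i. A subject's t_i is the shortest of three limits. The first is the time to the first event of that type. The second is tied to dosing and reads "duration of study treatment plus the 16-week washout period (approximately corresponding to five half-lives) after last treatment dose, or". The third is a calendar limit common to all subjects, worded as "end of the analysis period (week 64 for all safety follow-up".

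The SAP has the final visit "with the final visit (Visit 1999) occurring 16 weeks after the last treatment dose" (SAP 1.1), and an AE starting "within 16 weeks of the last dose will be considered as a treatment emergent adverse event" (SAP 2.5.1). The crude count is made "regardless of the treatment duration and/or study duration of each subject" (SAP 2.5.3).

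The SAP uses individual end dates elsewhere. For an AE end date with a missing month, "then the imputed end date should be set to the earliest of the study end date, 31DECYYYY or date of death" (SAP 5.2.2). SAP 2.6.2 censors its time-to-event analyses at the last non-missing weekly score. For each epoch, including follow-up, "the overall number of patients who entered, completed, and discontinued that phase will be summarized" (SAP 2.3.1).

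**The concern.** Person-time at risk should end when a subject can no longer contribute an observed event. None of the three limits does this for someone who leaves the study, or dies, before last dose + 16 weeks. The third cannot be read as the subject's own study end, because its parenthesis fixes it at week 64. No other section adds a stop: SAP 2.5.3 concerns only the count of subjects, and SAP 5.1 sets an end-of-treatment date with no cap at exit or death.

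The protocol provides for such exits:

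- withdrawal of consent, after which later data count as missing (Protocol 9.1.2);
- loss to follow-up (9.1.3);
- omalizumab use in the follow-up period, which ends participation without a safety assessment at the end-of-study visit (9.1.1).

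SAEs reported after the last visit go to the sponsor's safety database and not the eCRF (10.1.3). Such an event can therefore be absent from the numerator while its time remains in the denominator.

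Subjects who only stop treatment are not the problem. Protocol 9.1.1 expects them at all follow-up visits through Visit 1999, so their 16 weeks are observed.

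Apart from the Kaplan-Meier curve for injection site reactions, the EAIR is the planned AE output that accounts for unequal follow-up. As written, it does so for early treatment stop but not for early study exit. The error lowers the reported rates in a study whose primary objective is safety.

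**Working it through.** The documents state no EAIR or person-time figure to reproduce. The figures they do give agree with their own arithmetic: 65 × 0.90 = 58.5, against 58 stated (SAP 3.1), and last dose at Week 48 + 16 = Week 64.

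**Inputs**

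- From the documents: N = 65; last dose + 16 weeks; week 64 cap; exact Poisson limits (SAP 2.7.1.1).
- Assumed: number of leavers k; their mean last dose at Week 24; 4 weeks observed after it; all others observed for 64 weeks; events rare enough to leave person-time unchanged. The 10% drop-out in SAP 3.1 concerns one-year exposure and not study exit, so k = 7 serves only as an upper case.

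**Formulas**

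- SAP person-time = (65 − k) × 64 + k × (24 + 16)
- Observed person-time = (65 − k) × 64 + k × (24 + weeks observed after last dose)
- Understatement of the EAIR = 1 − observed / SAP

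| Leavers | Weeks observed after last dose | Observed subject-weeks | SAP subject-weeks | Understatement |
|---|---|---|---|---|
| 1 | 4 | 64×64 + 28 = 4124 | 64×64 + 40 = 4136 | 0.3% |
| 3 | 4 | 62×64 + 84 = 4052 | 62×64 + 120 = 4088 | 0.9% |
| 7 | 4 | 58×64 + 196 = 3908 | 58×64 + 280 = 3992 | 2.1% |
| 7 | 0 | 58×64 + 168 = 3880 | 3992 | 2.8% |

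**Sensitivity to timing.** With 7 leavers and 4 weeks observed, a mean last dose at Week 8 gives 1 − 3796/3880 = 2.2%, and at Week 40 gives 1 − 4020/4104 = 2.0%. For 3 subjects who take all doses (last at Week 48) and leave in follow-up, SAP time is 65 × 64 = 4160. Exit at Week 52 gives 1 − 4124/4160 = 0.9%, at Week 56 1 − 4136/4160 = 0.6%, and at Week 60 1 − 4148/4160 = 0.3%.

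**Effect on reported values.** These use the limits in SAP 2.7.1.1: lower 0.5·χ²(0.025; 2n)/Σt, upper 0.5·χ²(0.975; 2n+2)/Σt. They are per 100 patient-years at 52.1775 weeks per year, with 4 weeks observed.

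| Events | Leavers | Time stopped at exit | SAP rule |
|---|---|---|---|
| 2 | 3 | 2.58 (0.31–9.30) | 2.55 (0.31–9.22) |
| 2 | 7 | 2.67 (0.32–9.65) | 2.61 (0.32–9.44) |
| 0 | 3 | upper limit 4.75 | upper limit 4.71 |
| 0 | 7 | upper limit 4.93 | upper limit 4.82 |

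**The case against.** The strongest objection is that the effect is immaterial. With 2 events and 3 leavers the interval runs from about 0.3 to 9.3, and the correction moves the rate by 0.9%. The study has one arm and no safety hypothesis, the EAIR is descriptive, and the primary count does not use t_i. All of this stands, and it sets the severity.

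A second objection is that the protocol already narrows the gap. Protocol 10.1.1 asks for AE monitoring for at least 30 days after the last dose or end-of-study visit, whichever is longer. Suppose a leaver other than a consent withdrawal has an exit visit 4 weeks after the last dose. AEs are then due to 4 + 30/7 ≈ 8.3 weeks, and the gap is about 7.7 weeks instead of 12:

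- 3 leavers: 3 × 7.7 / 4088 ≈ 0.6%;
- 7 leavers: 7 × 7.7 / 3992 ≈ 1.4%;
- exit at Week 60: the gap closes, since 60 + 4.3 passes week 64.

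This is fair. It lowers the figures for such subjects but leaves them within the 0–2.8% range. It does not help after consent withdrawal, and the SAP does not tie t_i to this monitoring.

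A third objection is that the second limit is not as clear as last dose + 16 weeks. SAP 2.7.1.1 does not define treatment duration, and SAP 2.4.1 already adds 28 days when it defines exposure. Combining the two would put the limit at last dose + 20 weeks. Read with SAP 1.1 and 2.5.1, last dose + 16 weeks is the sensible meaning. The other reading would only enlarge the error: for 7 subjects leaving at a Week 24 last dose, 1 − 3880/4020 = 3.5%. The wording should settle this.

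**Conclusion.** The concern holds. Followed literally, SAP 2.7.1.1 credits unobserved time to event-free subjects who leave or die before last dose + 16 weeks. The direction is known: non-zero rates and upper limits come out too low.

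Under the stated assumptions the understatement is about 0.3% per leaver. It ranges from 0%, if all discontinuers complete follow-up, to 2.8%, if 7 subjects exit at a Week 24 last dose. The number and timing of true study leavers are not in the documents, so these are illustrations, not forecasts.

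The point is minor. The intervals are far wider than the shift, the EAIR is descriptive, and the primary count is untouched. It is still worth correcting, because the rate was introduced to handle differing study participation and the correction is cheap.

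**What to change.** In SAP 2.7.1.1, define t_i as running to the earliest of:

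- the first event of that type;
- last dose date + 112 days (which also removes the ambiguity about treatment duration);
- week 64;
- the subject's actual end of AE collection in the clinical database, meaning date of death, consent withdrawal, or last contact at which AEs were collected.

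An early end-of-study visit should not itself be a stop if AEs are still collected after it. Count in the EAIR numerator only events with onset on or before that same date, so that no event falls after its own t_i.

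The cost is a sentence or two in the SAP and one derived date. Study end and death dates are already used in SAP 5.2.2. The last AE-collection contact is not yet a defined SAP variable, so its derivation must be specified for subjects followed after an exit visit. No new data are needed, and the design and primary analysis do not change. The only downside is slightly higher non-zero rates and upper limits.
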